1.2 Synopsis

International Co-ordinating Investigators:

[name] PhD Center for Cancer Research National Cancer Institute [name][name] 20892

Protocol Title:

A Phase 2, Open-Label, Randomized Study of the Efficacy and Safety of Acalabrutinib with Best Supportive Care Versus Best Supportive Care in Subjects Hospitalized with COVID-19

Rationale:

Coronavirus disease 2019 (COVID-19) is a new pandemic disease caused by the severe acute respiratory syndrome coronavirus 2 (SARS-CoV-2). Most COVID-19 cases (~80%) are mild respiratory illnesses. However, the some require hospitalization (mostly due to pneumonia) and can progress quickly to severe acute lung injury and acute respiratory distress syndrome (ARDS) (Huang et al 2020, Wu and McGoogan 2020, Zhou et al 2020), which is associated with high mortality. A viral-induced cytokine storm or "hyperimmune response" is hypothesized to be a major pathogenic mechanism of ARDS in these patients through modulation of pulmonary macrophages and dendritic cells (Channappanavar et al 2016, Huang et al 2005, Wong et al 2004, Yoshikawa et al 2009) and/or neutrophils (Herold et al 2015). Putative inflammatory mediators include interleukin (IL)-1 β , IL-6, IL-8, IL-10, tumor necrosis factor alpha (TNF α), and monocyte chemoattractant protein-1 (MCP-1) (Chen et al 2020, Herold et al 2015, Yoshikawa et al 2009).

Bruton's tyrosine kinase (Btk) is a Tec family non-receptor protein kinase, expressed in B cells, myeloid cells, osteoclasts, mast cells and platelets. The function of Btk in signaling pathways activated by the engagement of the B-cell receptor has been well established (Buggy and Elias 2012). Btk is also involved in the following biologic processes: Fc gamma receptor signaling in myeloid cells, mast cell degranulation, osteoclast differentiation, and signaling through Toll-like receptors (TLRs) in macrophages and neutrophils. Btk inhibition is associated with a decrease in proinflammatory cytokines in patients with hematologic malignancies.

Acalabrutinib is a covalent Btk inhibitor with greater selectivity and better physiochemical properties than ibrutinib and other Btk inhibitors currently in development. Acalabrutinib is currently approved in the United States for the treatment of patients with mantle cell lymphoma or chronic lymphocytic leukemia/small lymphocytic lymphoma [Calquence® prescribing information]. Patients with hematologic malignancies treated with acalabrutinib

have shown statistically significant decreases in the following cytokines: TNF α (p<0.001), IL-10 (p<0.001), and MCP-1 (p<0.01) (Byrd et al 2016) and IL-6 (p<0.05) (data on file). Decreasing these immunomodulating cytokines in patients with COVID-19 may mitigate the pathophysiologic response that leads to the most severe morbidity and mortality associated with viral infection. Recently, encouraging results were reported in a case series of patients hospitalized with severe COVID-19 and treated with acalabrutinib led by investigators at the National Institutes of Health (Roschewski 2020). Similarly, other BTK inhibitors have shown promise in COVID-19 patients with hematologic malignancies (Thibaud et al 2020, Treon et al 2020).

The purpose of this Phase 2 study is to evaluate the safety and preliminary efficacy of adding acalabrutinib to best supportive care (BSC) for subjects with life-threatening COVID-19 symptoms.

Primary Objectives	Primary Endpoints/Variables
 To evaluate the safety of acalabrutinib in subjects with COVID-19 when administered with BSC To evaluate the efficacy of adding acalabrutinib to BSC for the treatment of COVID-19 	 Safety Type, frequency, severity, and relationship to study treatment of any treatment-emergent adverse events (TEAEs) or abnormalities of laboratory tests, serious adverse events (SAEs), or adverse events (AEs) leading to discontinuation of study treatment. Efficacy Proportion of subjects alive and free of respiratory failure at Day 28 For the purpose of this study, respiratory failure is defined based on resource utilization of any of the following modalities: Endotracheal intubation and mechanical ventilation Oxygen delivered by high-flow nasal cannula (heated, humidified, oxygen delivered via reinforced nasal cannula at flow rates >20 L/min with fraction of delivered oxygen ≥0.5) Noninvasive positive pressure ventilation or continuous positive airway pressure Extracorporeal membrane oxygenation
Secondary Efficacy Objectives	Secondary Efficacy Endpoints/Variables
To evaluate the efficacy of adding acalabrutinib to BSC for the treatment of COVID-19	 Proportion of subjects alive and free of respiratory failure (defined above) at Day 14

Objectives and Endpoints:

• Percent change from baseline in C-reactive protein (CRP; time frame: baseline, Days 3, 5, 7, 10, 14, 28)
• Change from baseline in ferritin (time frame: baseline, Days 3, 5, 7, 10, 14, 28)
• Change from baseline in absolute lymphocyte counts (time frame: baseline, Days 3, 5, 7, 10, 14, 28)
• All-cause mortality at Day 90
• Proportion of subjects alive and discharged from the intensive care unit (ICU) at Days 14 and 28
• Time from randomization to first occurrence of respiratory failure or death on study (up to 28 days after randomization) due to any cause
• Number of days alive and free of respiratory failure from randomization to 28 days after randomization
• Number of days with respiratory failure from randomization to 28 days after randomization
• Number of days hospitalized from randomization to 28 days after randomization
• Number of days in ICU (length of stay) from randomization to 90 days after randomization
• Number of days alive outside of hospital from randomization to 28 days after randomization
• Number of days alive outside of hospital from randomization to 90 days after randomization
 Relative change from baseline in oxygenation index (SpO₂/FiO₂) to Days 3, 5, 7, and 10
• Time to clinical improvement of at least 2 points (from randomization) on a 9-point category ordinal scale through Day 28 (see Section 8.8.1)
• Time to $SpO_2 > 94\%$ on room air

PK Endpoint/Variable
Summarized plasma concentrations of acalabrutinib and ACP-5862 at specified time points. PK parameters (eg, area under the concentration-time curve [AUC] and maximum observed concentration $[C_{max}]$) estimated, as appropriate.
Exploratory Endpoints/Variables

Overall Design:

This is a multicenter, randomized, open-label, Phase 2 study that will evaluate acalabrutinib plus BSC versus BSC in subjects with COVID-19 who are hospitalized.

Subjects will be randomly assigned (1:1) to receive one of the following 2 treatments:

- Arm 1: Acalabrutinib 100 mg twice daily (bid) \times 10 days + BSC (n=30)
- Arm 2: BSC alone (n=30)

For the purpose of this study, BSC is per discretion of the Investigator and institutional guidelines. However, refer to Section 5.2 and Section 6.5.3 for prohibited or restricted concomitant therapy. Subjects will be randomized based on the following stratification factors, which are considered prognostic factors for poor outcome:

- Age ($\geq 65 \text{ vs} < 65 \text{ years}$)
- Comorbidities (present vs absent). "Present" is defined as having at least 1 of the following comorbidities:
 - Cardiovascular disease, as defined by either heart failure New York Heart Association class ≥2 or hypertension requiring treatment
 - Diabetes mellitus requiring treatment
 - Chronic obstructive pulmonary disease or asthma requiring treatment
 - Current active solid tumor or hematologic malignancy

Inclusion/exclusion criteria are provided in Section 5. Assessments are provided in Section 1.1.

Study Period:

Estimated date of first subject enrolled Q2 2020.

Estimated date of last subject completed is Q3 2020.

Number of Subjects:

The total number of subjects to be randomized in this study is 60.

Treatments and Treatment Duration:

Acalabrutinib treatment should be administered within 6 hours of randomization on Day 1.

Subjects will take acalabrutinib 100 mg capsules by mouth bid for 10 days (a maximum of 20 doses). Capsules will be taken with water. The capsules should be swallowed intact and subjects should not attempt to open capsules or dissolve them in water.

Subjects on concomitant proton-pump inhibitors (PPIs) must take acalabrutinib with at least 100 mL of COCA-COLA[®] at room temperature. Other cola beverages (eg, Diet Coke[®], COCA-COLA Zero Sugar) or juices are not permitted. The capsules should be swallowed intact and subjects should not attempt to open capsules or dissolve them in COCA-COLA. **NOTE:** COCA-COLA contains glucose (5 g per 100 mL). Blood glucose levels of diabetic subjects must be monitored as clinically indicated and blood glucose-lowering medications adjusted accordingly.

Acalabrutinib can be taken with or without food.

Retreatment with acalabrutinib is not allowed.

BSC will be administered in both arms per Investigator's discretion and institutional guidelines.

Refer to Section 6.1 for additional information on treatments administered.

Internal Data Monitoring Committee:

This study will have an internal Data Monitoring Committee (iDMC), independent from the Sponsor's study team. Details of the roles and responsibilities of the iDMC and the safety and efficacy review will be provided in a separate iDMC charter. The iDMC will be responsible for reviewing the safety data periodically, enable early identification of safety signals in the study, minimize risk to subjects during the study, and make recommendations according to

prespecified stopping rules for safety, and as to the future conduct of this study in accordance with the iDMC charter (refer to Section 4.4 for details).

Statistical Methods:

In general, continuous data will be summarized using descriptive statistics (number of observations, mean, standard deviation, median, minimum, and maximum). Frequencies and percentages will be used for summarizing categorical (discrete) data.

Safety will be summarized for the treated population (Safety population) and will be based on the treatment they actually received. In this study, treatment is either acalabrutinib + BSC or BSC only. If a subject receives at least 1 dose of acalabrutinib, the subject is considered as acalabrutinib-treated, regardless to which arm the subject was randomized. Safety assessments will consist of monitoring and recording AEs, SAEs, and AEs leading to discontinuation of study treatment; measurements of protocol-specified hematology, clinical chemistry, and other laboratory variables; measurement of protocol-specified vital signs; and other protocol-specified tests that are deemed critical to the safety evaluation of the study treatment.

[figure not shown]
For subjects randomized to Arms 1 or 2, efficacy will be summarized for the intent-to-treat (ITT) population, which is defined as all subjects who were randomized, to be analyzed according to the arm to which they are randomly assigned, following "intent-to-treat" principle. An estimate of the primary endpoint, the proportion of subjects who are alive and free of respiratory failure at Day 28 and its 90% confidence interval (CI; using Wald method with continuity correction) will be calculated for each treatment arm. The Cochran-Mantel-Haenszel $\chi 2$ test stratified by age ($\geq 65 \text{ vs} < 65 \text{ years}$) and comorbidities (present vs absent) will be used to compare the proportion of subjects who are alive and free of respiratory failure at Day 28 between the two treatment arms. An unstratified analysis will also be performed. Finally, the difference in the proportion of subjects who are alive and free of respiratory failure at Day 28 will also be provided with 90% CIs. The treatment difference will be also estimated using a logistic regression (Ge 2011) with indicators for treatment and the randomization stratification factors (2 × 2) as well as baseline respiratory failure (with vs without).

Refer to Section 9 for additional details.

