8.4 Clinical Assessments During Hospitalization

8.4.1 Oxygen Treatments and Ventilator Use

If a subject requires oxygen supplementation, data will be recorded, including method of oxygen supplementation, maximum daily flow rate and fraction of inspired oxygen (FiO₂).

If a subject requires mechanical ventilation, data will be recorded regarding whether ventilator weaning was attempted.

For subjects on mechanical ventilation the following ventilator settings will be recorded: tidal volume, FiO2, peak airway pressure over the last 24 hours, plateau pressure, positive end expiratory pressure, and respiratory rate. The data will be recorded qd, and the worst value of the day will be entered

For subjects on mechanical ventilation, an arterial blood gas (pH, partial pressure of oxygen [PaO₂], partial pressure of carbon dioxide [PaCO₂], and FiO₂ at the time the sample was obtained), will be recorded qd. If more than one value is obtained for the arterial blood gases, the value closest to 08:00 will be used.

Arterial gasses should be collected from subjects if the sample is easily accessible and the procedure will not be painful to subjects (ie, subject is in the ICU or has arterial port). All available data from the arterial gases should be entered into the database. If the collection of arterial gases is not clinically indicated, the test should not be performed.

Predicted body weight will be recorded on the ventilator eCRF for assessment of tidal volume.

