8.4.2 Modified Sequential Organ Failure Assessment (SOFA) Scores

A modified SOFA score will be calculated. For each of the following routine assessments, the worst value of the day will be recorded in the eCRF: PaO_2/FiO_2 (mmHg) or oxygen saturation by pulse oximetry (SpO₂)/FiO₂ (mmHg), platelet count, bilirubin, vasopressor use (µg/kg/min, mmHg), and creatinine ([or urine output]). For laboratory values, use last available (if within 48 hours). On days when laboratory results are unavailable, values will be extrapolated from the previously available values.

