3.1.15 Relative change from baseline in oxygenation index

This is defined as the percentage change from baseline in oxygenation index (SpO_2/FiO_2) to Days 3, 5, 7 and 10. For this endpoint, baseline is defined as the observation on the date of randomization (Day 1) only.

Oxygenation index is calculated as

$$SpO_2 [\%] / FiO_2 [\text{decimal}]$$

It will be calculated for the baseline and each post-baseline assessment using the SpO_2 (oxygen saturation) value and the FiO_2 (fraction of inspired oxygen) value collected or derived on the VS and OXYGEN or VENTUSE eCRF pages, respectively. Details on these variables and visit windows are provided in Section 3.2.6 and Section 4.1, respectively.

3.1.16 Time to clinical improvement of at least 2 points (from randomization) on a 9-point category ordinal scale through Day 28

This is defined as the time (in days) from randomization to the date of first demonstrated clinical improvement of at least 2 points (i.e., a decline of two points) on the following 9-point category ordinal scale through Day 28:

0. * Uninfected, no clinical or virological evidence of infection
1. Ambulatory, no limitation of activities
2. Ambulatory, limitation of activities
3. Hospitalized – mild disease, no oxygen therapy
4. Hospitalized – mild disease, oxygen by mask or nasal prongs
5. Hospitalized – severe disease, non-invasive ventilation or high flow oxygen
6. Hospitalised – severe disease, intubation and mechanical ventilation
7. Hospitalized – severe disease, ventilation and additional organ support, such as pressors, renal replacement therapy, extracorporeal membrane oxygenation
8. Death

*Score of zero on 9-point category ordinal scale will not be evaluated in this study.

This information will be collected in the OSCI pages in the eCRF as per the SoA in the CSP.

Baseline ordinal scale score is defined as the result obtained on the date of randomization (Day 1) only.

If a subject does not have an event (i.e., does not demonstrate clinical improvement of at least 2 points) on or before Day 28 and does not withdraw or become lost to follow up from the study on or prior to Day 28, the data will be censored at Day 28. If a subject does not have an event but withdraws from the study or is lost to follow up on or prior to Day 28, the data will be censored at the last date known that the subject has not demonstrated clinical improvement of at least 2 points up to Day 28.

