3.2.6 Oxygen treatment, ventilator use and mSOFA score

If a subject requires oxygen supplementation, data will be recorded, including method of oxygen supplementation and maximum daily flow rate. Fraction of inspired oxygen [FiO_2] will be reported or derived.

For subjects using a nasal cannula or simple mask, the maximum daily flow rate will be entered into the OXYGEN or VENTUSE eCRF and FiO_2 will be derived as per the conversion guidelines in Section 8.3. Note that the conversion is different depending on whether the subject is on a mask or nasal cannula. For subjects on high-flow oxygen therapy or using other types of masks, FiO_2 will be entered directly into the OXYGEN eCRF page. If FiO_2 is entered when a simple mask is selected as the method of oxygen, the value entered in the database will be used instead of deriving the value. For subjects on high-flow oxygen therapy or using other types of masks, FiO_2 will be entered directly into the OXYGEN eCRF page. For subjects on mechanical ventilation, FiO_2 will be entered directly into the VENTUSE eCRF page.

Since FiO_2 is only collected on days that oxygen or mechanical ventilation is used, FiO_2 will be imputed for days that no oxygen or mechanical ventilation is reported. If a subject has no oxygen or mechanical ventilation reported on a given day (method of oxygen (MOXDEL) is blank in the OXYGEN form and type of assisted ventilation (ASSVENTT) is blank in the VENTUSE form) then FiO_2 will be imputed as 21%.

If a subject requires mechanical ventilation, data will be recorded regarding whether ventilator weaning was attempted. For subjects on mechanical ventilation the following ventilator settings will be recorded: tidal volume, FiO_2 , peak airway pressure over the last 24 hours, plateau pressure, positive end expiratory pressure, and respiratory rate. Predicted body weight will be recorded assessment of tidal volume. The data will be recorded daily, and the worst value of the day will be entered in the eCRF.

For subjects on mechanical ventilation, an arterial blood gas (pH, oxygen, carbon dioxide, oxygen saturation and bicarbonate), if available, will be recorded daily.

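### SAP 3.1.15 forms SpO2/FiO2 from two values that are not linked in time, so the oxygenation index is distorted on days when oxygen flow changes

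*Protocol*

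**What the plan says.** The endpoint in Protocol 1.2 and Section 3 is "Relative change from baseline in oxygenation index", at Days 3, 5, 7 and 10. SAP 3.1.15 defines it as a percentage change in SpO2 (in %) divided by FiO2 (as a decimal), with a Day 1 baseline only. The SAP says of the index: "It will be calculated for the baseline and each post-baseline assessment". The two components are "collected or derived on the VS and OXYGEN or VENTUSE eCRF pages, respectively".

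**FiO2.** Protocol 8.4.1 has sites record "method of oxygen supplementation, maximum daily flow rate and fraction of inspired oxygen". SAP 3.2.6 adds: "For subjects using a nasal cannula or simple mask, the maximum daily flow rate will be entered into the OXYGEN or VENTUSE eCRF". FiO2 is then derived from that flow by the conversion in SAP 8.3, unless FiO2 was entered directly for a simple mask. For high-flow oxygen and other masks FiO2 is entered directly, with no time of day given. For ventilated subjects the entry is the day's worst value. The room-air value of 21% is imputed only when the whole day has no oxygen or ventilation entry.

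**SpO2.** SAP 4.1 uses the worst value when a day has several observations and, for vital signs, equates worst with the highest value. It makes no exception for SpO2.

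**Where FiO2 is tied to its partner.** For blood gases in ventilated subjects, Protocol 8.4.1 asks for the FiO2 in use when the sample was drawn. For the modified SOFA score, Protocol 8.4.2 treats the oxygenation ratio as one item, of which "the worst value of the day will be recorded in the eCRF". SAP 3.1.15 draws on neither.

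**The concern.** A ratio of saturation to inspired oxygen describes gas exchange only if both values hold at the same moment. Here the denominator reflects the peak oxygen need of the calendar day, while the numerator is a reading taken at an unspecified time. If there are several readings, it is the best one, because a high SpO2 is good, not bad. A subject who needed 6 L/min overnight and is on room air by the time of the reading gets a good saturation divided by the overnight FiO2, a ratio that may have held at no point in the day.

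The mismatch is largest on days when oxygen is being reduced, which are the days the endpoint should register. It also affects the Day 1 baseline, which enters every later percent change. At stake is whether a table of this index can be read as the course of oxygenation.

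**Working it through.** **Inputs.** Cannula: FiO2 % = 4 × flow + 20. Simple mask: FiO2 % = max(6 × flow − 1, 24) below 10 L/min and 6 × flow from 10 L/min (both SAP 8.3). Room air: 21% (SAP 3.2.6).

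**Reproducing the SAP's figures.** The cannula formula at 1 to 6 L/min gives 24, 28, 32, 36, 40 and 44%. The mask formula at 6 to 10 L/min gives 35, 41, 47, 53 and 60%. All 11 tabulated values agree.

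**Error in one day's index.** Let F_max be the FiO2 from the day's highest flow and F_read the FiO2 in use at the SpO2 reading. The same SpO2 stands over both, so it cancels:

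understatement = 1 − F_read / F_max

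| Day's maximum → at the reading | Calculation | Understated by |
|---|---|---|
| Cannula 3 → 2 L/min | 1 − 28/32 | 12.5% |
| Cannula 4 → 2 L/min | 1 − 28/36 | 22.2% |
| Cannula 6 → 3 L/min | 1 − 32/44 | 27.3% |
| Cannula 6 → 1 L/min | 1 − 24/44 | 45.5% |
| Cannula 6 L/min → room air | 1 − 21/44 | 52.3% |
| Simple mask 10 L/min → room air | 1 − 21/60 | 65.0% |
| Constant flow, or room air all day | F_read = F_max | 0% |

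With an assumed SpO2 of 95%, the fifth row is an index of 95/0.44 = 216 in place of 95/0.21 = 452.

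**Effect of taking the highest SpO2.** This rule raises the numerator and so offsets part of the error, but only a little. Suppose 98% is used where 90% was the saturation on room air (assumed values). The 52.3% then becomes 1 − (98/0.44)/(90/0.21) = 48.0%.

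**Error in the percent change, which is the endpoint** (SpO2 held constant):

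- *Blunted.* Day 1 is steady at 6 L/min. On the assessment day the maximum is 6 L/min and the reading is on room air. The SAP rule gives 0.44/0.44 − 1 = 0%. Matched values give 0.44/0.21 − 1 = +110%.
- *Inflated.* On Day 1 the maximum is 6 L/min but the reading is at 3 L/min. Flow is then steady at 3 L/min. The SAP rule gives 0.44/0.32 − 1 = +37.5%. Matched values give 0.32/0.32 − 1 = 0%.
- *Cancelled.* If F_read/F_max is the same on both days, the percent change is correct.

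**The case against.** The strongest reply is that recording the worst value of the day is a consistent convention in these documents, that it applies equally to both arms, and that little depends on this endpoint. SAP 4.3.2.14 plans only summary statistics, plots and a listing. The index is not among the DMC outputs in SAP 8.2. Recovery is also measured by the ordinal scale and by time to SpO2 above 94% on room air. All of this stands and limits the weight of the point. It does not rescue the definition: pairing the day's highest SpO2 with the FiO2 of the day's highest flow is neither a worst-of-day ratio nor a simultaneous one.

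Four stronger readings are tempting, and the documents do not support them:

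- *The index is generally wrong by about half.* That size needs a wean from 6 L/min to room air, or nearly so, within one day and a reading at the low point. Modest steps give 12% to 27%. The maximum-flow derivation covers only cannula and simple mask, and an FiO2 entered for a mask overrides it.
- *Recovery is always registered late.* The sign depends on Day 1: the change can be blunted, inflated or correct.
- *The comparison between arms is biased or diluted by a known amount.* Bias would need same-day flow changes to differ between arms. The documents say nothing on this, nor on the share of days affected.
- *The modified SOFA ratio is a ready substitute.* Protocol 8.4.2 allows PaO2/FiO2 instead of SpO2/FiO2, and SAP 3.2.6 confines the score to subjects admitted to ICU. A worst-of-day ratio would also still miss same-day weaning.

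**Conclusion.** The point holds. SAP 3.1.15 combines two values with no link in time, and the maximum rule in SAP 4.1 selects the best SpO2 under the name of the worst. On days when cannula flow falls, the index is understated by 12.5% to 27.3% for the modest steps shown and by 52.3% for 6 L/min to room air; a simple mask can give more. Days of constant flow and full room-air days are free of the error. For the percent change, the worked cases run from 0% reported instead of +110% to +37.5% reported instead of 0%.

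These sizes rest on the SAP 8.3 conversion and on assumed flow patterns, with SpO2 read at the lower flow. If SpO2 was read at the day's peak flow, there is no error. Since the frequency of such days is not given and the rule is common to both arms, the supported conclusion is added noise and distorted percent changes in a descriptive secondary endpoint. It merits correction but does not touch the primary analysis.

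**What to change.** **Preferred.** On the vital-signs page, record the oxygen device and the flow or FiO2 in use at the SpO2 reading. In SAP 3.1.15, compute the index, baseline included, only from that pair. In SAP 4.1, exempt SpO2 from the rule that the maximum is the worst value. The cost is one or two extra fields per daily reading and a short change of wording.

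**If data collection can no longer change.** SAP 1.3 reports recruitment complete with 62 subjects randomized, so this may be the practical route. Use the day's lowest recorded SpO2 with the FiO2 from the day's maximum flow, at baseline and afterwards. Label the endpoint a worst-case daily SpO2/FiO2 and state that it does not reflect same-day weaning. This costs SAP wording and programming only. It makes the index consistent and honestly named but does not restore sensitivity on weaning days. Do not rely on the modified SOFA ratio, which may not exist for subjects outside the ICU.
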